### **2.4.6 Analyses of pharmacokinetic**

#### **2.4.6.1 Pharmacokinetic variables**

The population PK of isatuximab will be characterized in the population of patients using a nonlinear mixed effect modeling approach by MONOLIX software version 2016 R1 (or more recent version) (Lixoft). Both rich and sparse sampling PK data available from Phase 1, 2 and

possibly phase 3 studies will be used for the analysis. Additional details of the analysis plan (Population PK Analysis Plan) and the results will be provided in a separate document. The population estimates from this analysis will provide a prior distribution from which individual Bayesian estimates of the PK parameters and of individual exposure ( $C_{max}$ ,  $C_{trough}$  and cumulated AUC) for each patient in this study will be derived.

Pharmacokinetic parameters of isatuximab (listed in [Section 2.1.5](#)) will be summarized by descriptive statistics (such as mean, geometric mean, median, standard deviation, standard error of mean, coefficient of variation, minimum, and maximum).

Predose dose concentration ( $C_{trough_{obs}}$ ) of isatuximab will be tabulated with standard descriptive statistics by visit (up to Cycle 10) and will be represented graphically as function of sampling time (day/cycle) over the study period to visualize the steady state achievement. A listing of  $C_{trough_{obs}}$  for individual patients will also be provided.  $C_{trough_{obs}}$  will be kept for the descriptive statistics if sampling occurs after 7 days  $\pm$  2 days from previous infusion for sampling done until Cycle 1 Day 22 and after 14 days  $\pm$  3 days from previous infusion for sampling done from Cycle 1 Day 22 up to Cycle 10.

Cycles in patients with dose delay and/or dose reduction, and samples with missing date and/or time and/or date and time of the previous dose, will be discarded from the analyses.

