1.6 FOOTNOTES FOR STUDY FLOWCHARTS

1. Evaluation: Assessments to be performed prior to study drug administration unless otherwise indicated. Results should be reviewed by the Investigator.
2. If the patient cannot be registered within 21 days of informed consent, the same patient may be re-screened after discussion with the sponsor, provided that there are no persisting safety concerns for patient's study participation. The informed consent form will have to be re-signed by the re-screened patient before starting re-screening procedures. New patient number will be given for the re-screened patients.
3. Cycle: A cycle is 28 days.
4. Allowance for Day 8, Day15 and Day 22 at first cycle is +/- 2 days. Allowance for Day 1 and Day15 at subsequent cycles are +/- 3 days.
5. The ICF should be signed before any study-related procedures or tests are initiated.
All patients who participated in Phase I part and is going to continue study treatment after completing Cycle 1 must sign a second ICF before commencing IMP administration in Cycle 2 Day1.
6. Demography: Includes date of birth, gender and race.
Medical/Surgical History: Includes relevant history of previous/associated pathologies other than multiple myeloma.
Disease History: Includes date of initial diagnosis of symptomatic MM, subtype, stage, previous anti-MM therapy (drug name by line of therapy, start and end date of administration, reason for discontinuation, best response and date of progression/relapse), disease status at inclusion (refractory to last IMiD or PI included therapy). In addition, results of additional procedures (such as karyotype, FISH, etc) performed as part of standard of care to assess the current disease status may also be collected. A patient card will be provided to the patient indicating he/she is receiving an anti-CD38 treatment and the site will notify its blood bank that the patient is receiving an anti-CD38 treatment.
7. Hospitalization: Day 1 through the entire day of the 3rd infusion (Day 15) hospitalization is recommended. Hospitalization will be expanded to the entire first cycle of the study treatment (ie. DLT observation period), if the investigator and the study committee judged appropriate.
8. Registration process can be completed in Day -1 however all eligibility criteria should be re-confirmed by investigators in Day 1 before IMP administration.

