1.8 PK FLOW CHART - PHASE II PART

Cycle	Cycle 1						Cycle 2			
	Day		D1	D8 (±2D)	D15 (±2D)		D22 (±2D)	D1 (±3D)		D15 (±3D)
Time (hour/minute)	0H (start infusion)	EoI	EoI + 1h	0H	0H	EoI	0H	EoI	0H	
Indicative clock time (example)	8 am	noon	1 pm	8 am	8 am	noon	8 am	8 am	8 am	
IMP administration										
isatuximab Administration	X-	-X		X	X-	-X	X	X-	-X	
Samples										
PK sampling	P00 ^b	P01 ^a	P02	P03 ^b	P04 ^b	P05 ^a	P06 ^b	P00 ^b	P01 ^a	
RD in Bone Marrow	Y00 ^c									
ADA	P00 ^b			P01 ^b	P02 ^b		P03 ^b	P00 ^b		
Cycle	Cycle 3		Cycle 4				Subsequent Cycles ^f		EoT	Follow-up
Day	D1 (±3D)	D15 (±3D)	D1 (±3D)			D15 (±3D)	D1 (±3D)	D15 (±3D)	30 days after last IMP (±7D)	60 days after last IMP (±7D)
Time (hour/minute)	0H	0H	0H	EoI	EoI + 1h	0H	0H	0H		
Indicative clock time (example)	8 am	8 am	8 am	noon	1 pm	8 am	8 am	8 am	8 am	8 am
IMP administration										
isatuximab Administration	X	X	X-	-X		X	X	X		
Samples										
PK sampling	P00 ^b	P01 ^b	P00 ^b	P01 ^a	P02	P03 ^b	P00 ^{b,e}	P01 ^{b,e}	PF0	
RD in Bone Marrow										
ADA	P00 ^b		P00 ^b				P00 ^{b,e}		PF0	PF1 ^d

EoI = End of Infusion; ADA = Anti-Drug Antibody; RD = CD38 receptor density; IMP = Investigational Medicinal Product; EoT: End of Treatment, P = Plasma, Y= Bone marrow, F = follow up

a Sample collected just before actual end of isatuximab infusion (within -5 min)

b Sample collected just before IMP administration.

c Required at screening/baseline (within 21 days prior to study drug administration).

d At 60 days, if patient is positive for ADA or the sample is inconclusive, additional ADA samples are required every 30 days (± 7 days) until sample is negative (sample ID: PF2, PF3 etc.).

e Sample collected up to 10 cycles. If ADA is positive at Cycle 10, one additional sampling for ADA evaluation should be collected 3 months later. No further ADA will be collected, even if the 3-month sample is positive.

f Post second analysis cut-off period, only ADA samples will be collected.

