8.1.2 Dose of Drug per Administration

Isatuximab will be administered once every week (QW) in Cycle 1 (4 weeks) followed by once every other week (Q2W) in subsequent cycle until unacceptable toxicity, disease progression, withdrawal of consent and/or Investigator's decision ([Section 1.2](#)). Cycle N day 1 corresponds to cycle N-1 day 29.

For dose level and schedule, refer to [Section 6.2.1](#).

The initial rate of infusion of isatuximab will be 175 mg/hour.

- First infusion:
Initiate infusion rate at 175 mg/hour. In the absence of infusion associated reaction after 1 hour of infusion, increase the rate by 50 mg/hour increments every 30 minutes, to a maximum of 400 mg/hour.
- Subsequent infusions:
Initiate infusion rate at 175 mg/hour. In the absence of infusion associated reaction after 1 hour of infusion, increase the rate by 100 mg/hour increments every 30 minutes, to a maximum of 400 mg/hour.

recovered, the infusion may be restarted at one half of the original infusion rates. If symptoms do not recur after 30 minutes, the infusion rate may be increased in 50 mg/hour increments every 30 minutes, to a maximum of 400 mg/hour.

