#### **2.1.5 Pharmacokinetic variables**

The PK sampling times were provided in the study flowcharts.

Isatuximab concentrations will be analyzed with the PKDMS software (Pharsight) using non-compartmental methods for all cohorts. The following PK parameters will be calculated following the first administration:

- Concentration observed at the end of an IV infusion ( $C_{eoi}$ )
- Maximum observed concentration ( $C_{max}$ )
- Time to reach  $C_{max}$  ( $t_{max}$ )
- Concentrations just before drug infusion ( $C_{trough}$ )
- AUC over the dosing interval ( $AUC_{1\text{week}}$ )

$C_{trough}$  are defined as sample collected before dosing of all cycles, and in a time window of 6 to 8 days after the previous start of infusion for the QW administration.

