#### **2.1.5 Pharmacokinetic variables**

Isatuximab plasma concentrations will be summarized and the following PK individual parameters will be calculated:

- Cumulative AUC over a 1, 2 or 4 week interval (AUC1W, AUC2W, AUC4W)
- $C_{\text{trough}}$  (pre-dose concentration) at 1, 2, 4 weeks
- $C_{\text{max}}$  at Cycle 1 Day 1, Cycle 2 Day 1 and Cycle 4 Day 1
- Clearance (CL)
- Accumulation ratios (AUCss/AUC1W). AUCss is AUC at steady state.

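### The Phase 2 SAP's observed-trough filter demands a gap of 14 ± 3 days at Cycle 2 Day 1, which falls 7 days after the previous infusion, so on-schedule end-of-loading troughs drop out of the by-visit table

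*SAP*

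**What the plan says.** Phase 2 SAP section 2.4.6.1 tabulates observed pre-dose isatuximab concentrations by visit up to Cycle 10. A value enters the descriptive statistics only if its gap from the previous infusion is acceptable. For samples up to Cycle 1 Day 22 the gap must be 7 ± 2 days. The second window, 14 ± 3 days, is counted "from previous infusion for sampling done from Cycle 1 Day 22 up to Cycle 10".

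The protocol fixes the calendar. Section 8.1.2 gives weekly dosing in Cycle 1 and two-weekly dosing afterwards, and adds: "Cycle N day 1 corresponds to cycle N-1 day 29". The Phase II PK flow chart (section 1.8) schedules a 0H sample at Cycle 2 Day 1 with the footnote "Sample collected just before IMP administration". Footnote 4 of section 1.6 sets the visit windows: "Allowance for Day 8, Day15 and Day 22 at first cycle is +/- 2 days", and "Allowance for Day 1 and Day15 at subsequent cycles are +/- 3 days".

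The Phase 1 SAP (section 2.1.5) words its trough window differently, taking samples before dosing of all cycles and "in a time window of 6 to 8 days after the previous start of infusion for the QW administration".

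**The concern.** The change from the 7-day to the 14-day rule is placed one visit too early. Dosing becomes two-weekly in Cycle 2, but the pre-dose sample at Cycle 2 Day 1 still looks back over a weekly interval. The first sample that looks back over 14 days is Cycle 2 Day 15. As written, the filter rejects Cycle 2 Day 1 samples taken on schedule and keeps only those with an atypically long gap.

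This visit gives the only scheduled observed trough after all four weekly infusions. Protocol section 4.4.3 reports that the week-4 trough predicted response in the earlier global study and uses that finding to support the weekly loading. Readers would expect observed data for that time point in the table.

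There is a second fault in the same sentence. Cycle 1 Day 22 is named in both rules, and their windows (5 to 9 days and 11 to 17 days) do not overlap, so that visit has no single defined rule.

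**Working it through.** **Inputs**
- Infusion days on the nominal schedule: 1, 8, 15, 22 (Cycle 1, weekly), then 29, 43, 57 and so on (Protocol 6.5 and 8.1.2).
- Filter windows: 7 ± 2 = 5 to 9 days; 14 ± 3 = 11 to 17 days (Phase 2 SAP 2.4.6.1).
- Visit windows: Day 22 ± 2 days; Cycle 2 Day 1 ± 3 days (Protocol 1.6, footnote 4).

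**Step 1. Nominal schedule.** Gap = day of the sample minus day of the previous infusion.

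| Visit | Study day | Gap (days) | Window assigned | Kept? |
|---|---|---|---|---|
| Cycle 1 Day 8 | 8 | 8 − 1 = 7 | 5–9 | yes |
| Cycle 1 Day 15 | 15 | 15 − 8 = 7 | 5–9 | yes |
| Cycle 1 Day 22 | 22 | 22 − 15 = 7 | 5–9 and 11–17 | yes by the first, no by the second |
| Cycle 2 Day 1 | 29 | 29 − 22 = 7 | 11–17 | **no** |
| Cycle 2 Day 15 | 43 | 43 − 29 = 14 | 11–17 | yes |
| Cycle 3 Day 1 | 57 | 57 − 43 = 14 | 11–17 | yes |

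**Step 2. Do the visit windows rescue it?** The Day 22 infusion may fall on days 20 to 24 (5 values) and Cycle 2 Day 1 on days 26 to 32 (7 values), giving 5 × 7 = 35 combinations. The gap runs from 26 − 24 = 2 to 32 − 20 = 12 days.

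| Gap (days) | 2 | 3 | 4 | 5 | 6 | 7 | 8 | 9 | 10 | 11 | 12 |
|---|---|---|---|---|---|---|---|---|---|---|---|
| Combinations | 1 | 2 | 3 | 4 | 5 | 5 | 5 | 4 | 3 | 2 | 1 |

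- 14 ± 3 (11 to 17 days): 2 + 1 = 3 of 35. These are Day 20 with Day 31, Day 20 with Day 32, and Day 21 with Day 32.
- 7 ± 2 (5 to 9 days): 4 + 5 + 5 + 5 + 4 = 23 of 35.
- 7 ± 3 (4 to 10 days): 23 + 3 + 3 = 29 of 35.

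These are unweighted counts of day combinations. They do not estimate the share of patients.

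**Step 3. Does another exclusion remove the three that pass?** Section 2.4.6.1 also discards cycles with a dose delay. Under section 2.4.3 a cycle is delayed if its start, minus 28, minus the start of the previous cycle, exceeds 3 days. With Cycle 1 starting on Day 1, the three combinations give 31 − 28 − 1 = 2 or 32 − 28 − 1 = 3 days. Neither exceeds 3, so all three stay in the table.

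**Step 4. Does another reading help?** Taking the second rule to begin after Day 22 settles the double rule at Day 22 but leaves Cycle 2 Day 1 under 14 ± 3. Treating Day 22 as the previous infusion instead of the sampling visit also puts the interval that follows it under 14 ± 3. No other passage exempts the visit.

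**Step 5. Comparison with the Phase 1 SAP.** Its 6 to 8 day window is tied to weekly administration. On its natural reading it accepts a 7-day gap at Cycle 2 Day 1, so the two SAPs treat the corresponding sample in opposite ways.

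**The case against.** The strongest reply is that this is a drafting slip with a small consequence. The sentence cannot be carried out literally at Day 22 either, so a programmer has to interpret it, and other parts of the same SAP point to the intent. Section 2.4.3 credits 7 days after the last dose of a weekly cycle and leaves Day 1 of a cycle out of its infusion-delay rule. At most one row of one secondary table is affected. The individual listing is still produced, and the week-4 trough parameter in section 2.1.5 comes from the population-PK estimates. The filter is stated for the descriptive statistics, so the plot is arguably outside it. The Phase 1 wording is loose and does not name Cycle 2 Day 1.

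Much of this stands as a limit on importance. The effect is narrow, the Phase 1 comparison depends on how that sentence is read, and the combination counts only illustrate the point. None of it changes the result, because the hints elsewhere do not amend section 2.4.6.1. A programmer who used the sensible rule would be departing from the written plan, and one who followed the plan would produce an empty or misleading row.

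**Conclusion.** The concern holds. On the nominal schedule the Cycle 2 Day 1 gap is 7 days against a required 11 to 17, so the on-schedule trough is left out of the by-visit descriptive statistics. Within the visit windows only gaps of 11 or 12 days survive, 3 of 35 combinations, and these do not represent the planned regimen. The overlap at Cycle 1 Day 22 is a separate ambiguity in the same sentence.

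The conclusion rests on the protocol's calendar and on reading the SAP sentence as written. It needs no assumption about patient data. Its reach is one row of a secondary descriptive table, and possibly the trough plot, since the SAP does not say whether the plot is filtered. The individual listing, the population-PK week-4 trough, ORR and the sample size are unaffected. The point should be corrected, but it does not threaten the trial's main conclusions.

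**What to change.** In Phase 2 SAP section 2.4.6.1:
- Apply the 7-day rule to samples through Cycle 2 Day 1. Extending the existing 7 ± 2 days is enough. If the sponsor wants to allow for that visit's wider window, 7 ± 3 days could be used at Cycle 2 Day 1 only.
- Start the 14 ± 3 day rule at Cycle 2 Day 15. This also leaves Cycle 1 Day 22 with a single rule.
- State whether the trough plot uses the filtered values.

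The cost is one sentence in the SAP and one programming condition, with no new samples. Protocol Appendix J (Amended Protocol 04) refers to a first analysis already performed. If a trough table was produced then under the present wording, it should be checked and rerun if needed. The documents do not show what was programmed.

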#### **2.4.7 Immune response**

Using the ADA evaluable population, the number (%) of patients will be provided for the following if at least one positive observed:

- Pre-existing ADA
- ADA negative at baseline
- On study ADA
  - Treatment-induced ADA
  - Persistent ADA
  - Transient ADA
  - Indeterminate ADA
  - Treatment boosted ADA
  - Last sample positive
- ADA prevalence
- ADA incidence

In addition, a data listing of each ADA sample result will be provided. The impact on PK, safety and efficacy endpoints may be further explored by graphical methods or descriptive, depending on the ADA prevalence.

## **2.4.8 Analyses of Biomarker variables**

### **2.4.8.1 Receptor density**

CD38 RD will be summarized with descriptive statistics for responders/non-responders. A responder is a patient with IAC assessment response  $\geq$  PR. In addition, summary of BOR will be provided by CD38 RD level and a graph showing ORR/non-responder rate (in y-axis) by CD38 RD level (ranging from 0 to 500 000 by increment of 1000 in x-axis) will be provided.

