#### 1.2.2 Secondary objectives

Secondary objectives of the phase 2 part of the study are:

- To evaluate the safety including immunogenicity of isatuximab. The severity, frequency and incidence of all adverse events will be assessed.
- To evaluate the pharmacokinetic (PK) profile of isatuximab in the proposed dosing schedule.
- To assess the relationship between baseline CD38 receptor density (RD) on MM cells and efficacy.

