### **1.3 DETERMINATION OF SAMPLE SIZE**

The phase 2 part of the study aims to evaluate 33-36 subjects which include the subjects in Phase 1 part at the dose level determined as MTD/recommended dose. Given an assumed true ORR of 28%, the null hypothesis ORR  $\leq 10\%$  will be rejected using an exact binomial test at a one-sided alpha of 0.025 with at least 80% power, if the observed ORR is greater than or equal to 24.2% (i.e., 8 responders). The sample size calculation was performed using SAS ver. 9.4 SAS/STAT 13.2, power procedure.

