##### ***2.4.4.1 Analysis of primary efficacy endpoint***

The primary analysis is based on the dose level determined as MTD combined in phase 1 and phase 2. ORR as assessed by IAC will be summarized. The null hypothesis that the true response rate (ORR) is <10% will be tested using a one-sided exact binomial test with a significance level of 0.025. A 95% two-sided confidence interval will be computed for ORR using Clopper-Pearson method.

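### The secondary objective on CD38 receptor density is analysed only descriptively, with no measure of association, no interval, and undefined density levels and graph rate

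*SAP*

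**What the plan says.** Phase 2 SAP 1.2.2 lists as a secondary objective "To assess the relationship between baseline CD38 receptor density (RD) on MM cells and efficacy". Protocol 5.2 has the same objective.

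Phase 2 SAP 2.4.8.1 plans three outputs:

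- "CD38 RD will be summarized with descriptive statistics for responders/non-responders", a responder being a patient with an IAC-assessed response of PR or better.
- A "summary of BOR will be provided by CD38 RD level". No levels or cut-points are given.
- A graph of the response and non-response rate "by CD38 RD level (ranging from 0 to 500 000 by increment of 1000 in x-axis) will be provided". The section does not say whether each plotted value is a rate within a 1000-unit step or a cumulative rate above or below a threshold.

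The section names no effect measure, interval, model or test. Protocol 13.4.7 says only that RD will be summarised by visit, and Protocol 13.4 makes analyses descriptive unless stated otherwise. On size, Phase 2 SAP 1.3 says "The phase 2 part of the study aims to evaluate 33-36 subjects which include the subjects in Phase 1 part" at the recommended dose, and assumes a true ORR of 28%.

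**The concern.** The objective asks about a relationship, but none of the three outputs is a planned estimate of one with its uncertainty. With about 10 responders, a similar RD in the two groups or a flat-looking graph could mean that density does not matter, or that the trial was too small to show that it does. The planned outputs do not tell the reader which.

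Two definitions are also left open. Without stated RD levels, cut-points for the response table could be chosen after responses are known. Without a definition of the rate, the same sentence leads to two quite different graphs, one of them close to uninformative at this sample size. Elsewhere the Phase 2 SAP is explicit: Table 4 in 2.1.3.1 gives subgroup cut-points (RD is not among them), and 2.4.8.2 lists the genotype categories.

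**Working it through.** **Inputs.** Graph range 0 to 500 000 and increment 1000: Phase 2 SAP 2.4.8.1. Sample size 33 to 36 and ORR 28%: Phase 2 SAP 1.3. Expected responders: 0.28 × 33 = 9.2 and 0.28 × 36 = 10.1. The RD distribution is in neither document, so it is assumed below and varied.

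**1. The plan's own sample-size figures.** The cut-off is 8/33 = 24.2%, as stated. The exact binomial probability of 8 or more responders at a true rate of 10% is 0.0141 (N = 33) to 0.0235 (N = 36), and 8 is the correct cut-off for every N from 33 to 36. Power at 28% is 74.5%, 77.6%, 80.5% and 83.0% for N = 33, 34, 35 and 36, so the stated 80% reproduces at 35 and 36 but not at 33 and 34. That is a separate matter. Only the ceiling of 36 patients and the 28% are used here.

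**2. The grid.** 500 000 / 1000 = 500 steps. At most 36/500 = 7.2% of steps can hold a patient, so at least 500 − 36 = 464 are empty and have no rate. With 10 responders, at most 10 steps can show a rate strictly between 0% and 100%.

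**3. The two readings of the graph.** If 36 values were spread evenly at random over the 500 steps, the expected number of patients alone in their step is 36 × (499/500)^35 = 33.6. The table gives simulated results (4000 runs, 28% response). It shows the share of occupied steps (within-step reading) or of defined grid points (cumulative reading, rate among patients at or above each value) that sit at exactly 0% or 100%. The lognormal cases use an SD of 0.6 on the natural-log scale.

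| Assumed RD distribution | Within step, N = 33 | Within step, N = 36 | Cumulative, N = 33 | Cumulative, N = 36 |
|---|---|---|---|---|
| Uniform 0–500 000 | 98.7% | 98.6% | 8.9% | 8.1% |
| Lognormal, median 150 000 | 97.4% | 97.2% | 24.7% | 23.5% |
| Lognormal, median 50 000 | 93.4% | 93.0% | 32.9% | 32.8% |
| Uniform 0–100 000 | 93.4% | 92.8% | 8.8% | 8.3% |
| Uniform 0–50 000 | 86.8% | 85.6% | 8.5% | 7.9% |

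**4. Precision of an explicit estimate.** For a logistic slope per SD of the predictor, SE ≈ 1/√(N × 0.28 × 0.72).

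- N = 36: 1/√7.26 = 0.371, and exp(1.96 × 0.371) = 2.07.
- N = 33: 1/√6.65 = 0.388, and exp(1.96 × 0.388) = 2.14.

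The 95% CI is therefore the odds ratio multiplied or divided by about 2.1. As a gauge, the odds ratio per SD detectable with 80% power at N = 36 is exp(2.80 × 0.371) = 2.83.

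**5. Per doubling.** The SE per doubling is the SE per SD divided by the SD of log2 RD, which the documents do not give. At N = 36, assumed SDs of 0.5, 1.0 and 1.5 give SEs of 0.742, 0.371 and 0.247, and CI factors of 4.3, 2.1 and 1.6.

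**The case against.** The strongest reply is that description is the declared approach. Protocol 13.4 says so, the objective promises neither a model nor a test, and about 10 responders cannot support much modelling. Comparing RD between responders and non-responders does bear on the relationship. Given n, mean and SD in each group, a reader could derive a difference and an interval: with 10 against 26 patients the half-width is 1.96 × √(1/10 + 1/26) = 0.73 SD. A model may also end in an inconclusive interval.

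Much of this stands. No hypothesis test is needed, and the primary ORR analysis is untouched. But an odds ratio with an interval is estimation, which a descriptive default does not rule out: Phase 2 SAP 2.4.4.2 already gives CBR, another secondary endpoint, a Clopper-Pearson interval. Protocol 4.4.3 reports that the programme has modelled ORR against a continuous predictor, week-4 trough concentration. A wide interval is also the information the reader lacks, and leaving readers to derive it is not a plan.

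Two stronger readings are tempting, and the documents support neither. A reader might infer that nearly every plotted point must be 0% or 100%. That needs a within-step rate, which the SAP does not fix. Under a cumulative rate only about 8% to 33% of defined points are extreme, and even within steps most of the grid is empty rather than at 0% or 100%. A reader might also infer that the objective rests on the graph alone, or goes wholly unexamined. The graph is one of three outputs, and the responder comparison does address the question. What is missing is a specified association measure with its uncertainty.

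**Conclusion.** The point holds in this limited form. The RD objective is served only descriptively, the RD levels and the graph's rate are undefined, and no association estimate or interval is planned. This is true under either reading of the graph.

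The degeneracy of the graph is conditional. On a within-step rate, at least 464 of 500 steps are empty and about 86% to 99% of the occupied ones show 0% or 100%, across the five assumed distributions. On a cumulative rate the problem does not arise.

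The precision figure of about 2.1 either side per SD is a large-sample approximation. It assumes 28% response, a modest association and a usable marrow value in every patient, so missing samples would widen it. The consequence is confined to this secondary objective.

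**What to change.** In Phase 2 SAP 2.4.8.1:

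- Keep the descriptive summaries, and state the RD levels for the best-overall-response table before they are related to response.
- Add one pre-specified Firth logistic regression of IAC response (PR or better) on log2 baseline RD, with no other covariates. Report the odds ratio per doubling with its 95% CI, labelled as estimation and not as a test.
- Name the population: all patients treated at the recommended dose, from both parts, with a baseline RD value. Report how many lack one. Protocol 13.3.3 ties the RD analysis to patients with a PK parameter, so the choice should be explicit.
- Replace the 1000-unit grid with individual patient points and the fitted curve with its confidence band. If a threshold graph is kept as well, say that its rate is cumulative and in which direction.

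The cost is one small model and one figure. No new data are needed, because RD is already measured at screening and response is already adjudicated. The downside is a wide interval, whose width per doubling cannot be stated until the spread of log2 RD is known.
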